**5.3.3. Escape Arm**

Patients who require topical or systemic rescue treatment (Section 6.3) for atopic dermatitis during the Induction Period, or, are non-responders at Week 16, will be eligible for treatment in an Escape Arm where patients will receive lebrikizumab Q2W from Week 16 through Week 52. In addition, patients who do not maintain an acceptable response during the Maintenance Period (have an EASI score <50% of baseline), will be eligible for the Escape Arm.

To enter the Escape Arm, patients must have been compliant with study visits during the Induction Period or the Maintenance Period, respectively. Patients receiving systemic rescue medication (Section 6.3) will be required to washout for 5 half-lives prior to initiating treatment in the Escape Arm. All patients eligible for the Escape Arm will receive blinded loading doses, based on their prior treatment assignment (see Table 3 below), followed by 250 mg lebrikizumab Q2W through Week 52 on study in an open-label fashion. Patients in the Escape Arm must

comply with study visits every 4 weeks. Patients in the Escape Arm, not achieving or maintaining an EASI50 score after 8 weeks of treatment will be terminated from the trial.

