5.1.3.2. Maintenance Escape Period

[figure not shown]
Patients who do not achieve an IGA of 0 or 1 or an EASI-75 at Week 16, patients received topical or systemic rescue therapy between baseline to Week 16 and those patients not maintaining an EASI-50 response following re-randomization at Week 24, 32, 40, or 48 will be

assigned to an Escape Arm and receive lebrikizumab 250 mg as open-label treatment Q2W through Week 52. Patients not achieving an EASI-50 response in the Escape Arm after 8 weeks of treatment will be terminated from the study.

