6.1.3.3. Maintenance Escape Population

For Maintenance W16 Escape Population, the number and percentage of patients achieving or maintaining a categorical efficacy and health outcome responses will be summarized by treatment group for all scheduled visits, including Week 52. Selected continuous secondary efficacy and health outcomes measure score and change from baseline (or percent improvement) will be summarized by treatment group at all scheduled visits during Maintenance Period, including Week 52 using descriptive statistics (n, mean, SD, median, minimum, and maximum). No inferential statistics will be provided for this population.

For Maintenance W24-48 Escape Population who were treated with lebrikizumab 250 mg Q2W following loss of response (EASI-50 nonresponse), the number and percentage of patients regaining EASI-50 response or achieving EASI-75 will be summarized every 4 weeks after lebrikizumab 250 mg Q2W treatment. No inferential statistics will be provided for this population.

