6.2.2.3. Maintenance Supportive Estimand for Categorical Endpoints (Composite)

The maintenance supportive estimand for categorical endpoints only is a composite estimand representing the clinical question of interest: what is the difference between treatment conditions, i.e., Lebrikizumab vs Placebo, in the target patient population, in successful responses after 52

weeks achieved without use of topical or systemic rescue medication, treatment discontinuation or transferring to escape arm?

The maintenance supportive estimand for categorical endpoints is described by the following attributes:

- A. Population: Maintenance Primary Population as described in Section 6.1.1.
- B. Endpoint: apply to all major and other secondary categorical endpoints for Maintenance Period
- C. How to account for intercurrent events (ICEs)
 - a. Subjects who require any use of topical or systemic rescue medication, discontinue treatment after week 16, or transfer to escape arm will be considered as treatment failures, i.e., non-responder, after the ICEs. Therefore, composite strategy is used for these types of ICEs.
- D. Population-level summary: difference in response proportions between treatment conditions

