6.4.2.1. Maintenance Period MCMC-MI

The MCMC-MI will be used to handle missing data relative to the maintenance primary estimand (Hybrid) and maintenance supportive estimand (Hybrid) for both binary and continuous endpoints. Imputation will be conducted within each treatment group independently so the pattern of missing observations in one treatment group cannot influence missing value imputation in another. The SAS PROC MI with MCMC option will be used to conduct the MCMC-MI. The imputation model will include the relevant baseline and post-baseline.

For each imputation process, 25 datasets with imputations will be calculated. The initial seed values are given in [Table KGAB.6.7](#). Each complete data set will be analyzed with the specified analysis. The results from these analyses will be combined into a single inference using SAS PROC MIANALYZE.

Cochran-Mantel-Haenszel (CMH) test statistic will be transformed using the Wilson-Hilferty transformation and then standardized (Ratitch 2013) prior to combining them using SAS PROC

MIANALYZE. Details of combining estimates and test statistics for categorical endpoints with multiple imputation can be found in [Appendix 2](#).

The imputation and analysis will be conducted on Maintenance Primary Population only.

The derivation of binary responses related to EASI, IGA and Pruritus NRS for Maintenance Period will follow the derivation for Induction Period.

Table KGAB.6.10. Seed Values for MCMC-MI for Maintenance Period

Analysis	Seed values Lebrikizumab 250 mg Q2W/Q4W/ Placebo
IGA	12345
EASI	12346
Pruritus NRS score	12347

Abbreviations: EASI = Eczema Area and Severity Index score; IGA = Investigator's Global Assessment for AD; MCMC = Markov chain Monte Carlo multiple imputation; NRS = Numeric Rating Scale; Q2W = every 2 weeks; Q4W=every 4 weeks.

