6.4.2.2. Maintenance Period NRI

The nonresponder imputation (NRI) method will be used to handle missing data relative to the maintenance supportive estimand for categorical endpoints (composite). Patients who receive rescue medication (per Protocol Section 6.3), discontinue treatment, or transfer to escape arm will be set to non-response subsequent to this time through Week 52 Intermittent missing values will also be set to non-response.

Re-randomized patients without at least 1 postbaseline observation will also be defined as nonresponders for all visits for the NRI analysis.

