	Proportion of patients with EASI-75 after lebrikizumab retreatment	NA	Descriptive statistics	Maintenance W24-48 Escape Population	No comparisons. Every 4 weeks after escape and re-treated by lebrikizumab 250 mg Q2W	Secondary analysis
Body Surface Area (BSA) Affected by AD	Change from baseline in BSA score	Supportive Estimand (Hypothetical)	MMRM with observed data	ITT	Leb 250 mg Q2W vs PBO; Week 16 and all scheduled visits in Induction Period	Secondary analysis

Measure	Variable	Estimand (Section 6.2)	Analysis Method (Section 6.1)	Population (Section 6.1.1)	Comparison/Time Point	Analysis Type
		Maintenance Supportive Estimand (Hypothetical)	ANCOVA with LOCF	Maintenance Primary Population	Leb 250 mg Q2W vs PBO; Leb 250 mg Q4W vs PBO; all scheduled visits in Maintenance Period	Secondary analysis
		NA	Descriptive statistics	Maintenance W16 Escape Population	No comparisons. all scheduled visits in Maintenance Period	Secondary analysis
Pruritus Numeric Rating Scale (NRS)	Change from baseline in Pruritus NRS Percent Change from baseline in Pruritus NRS	Primary Estimand (Hybrid)	ANCOVA with MCMC-MI	ITT	Leb 250 mg Q2W vs PBO; Week 16 and all scheduled visits in Induction Period	Key secondary analysis: W16; Secondary analysis: other timepoints
		Supportive Estimand (Hypothetical)	MMRM with observed data	ITT	Leb 250 mg Q2W vs PBO; Week 16 and all scheduled visits in Induction Period	Supplementary analysis
		Maintenance Primary Estimand (Hybrid)	ANCOVA with MCMC-MI	Maintenance Primary Population	Leb 250 mg Q2W vs PBO; Leb 250 mg Q4W vs PBO;	Secondary analysis
		Maintenance Supportive Estimand (Hybrid)	ANCOVA with MCMC-MI			Supplementary analysis
		Maintenance Supportive Estimand (Hypothetical)	ANCOVA with LOCF			Supplementary analysis
		NA	Descriptive statistics	Maintenance W16 Escape Population	No comparisons. all scheduled visits in Maintenance Period	Secondary analysis

Measure	Variable	Estimand (Section 6.2)	Analysis Method (Section 6.1)	Population (Section 6.1.1)	Comparison/Time Point	Analysis Type
	Proportion of patients achieving at least 4-point improvement in pruritus NRS	Primary Estimand (Hybrid)	CMH analysis with MCMC-MI	ITT, ITT with Baseline Pruritus NRS score at least 4, ITT with Baseline Pruritus NRS score at least 5	Leb 250 mg Q2W vs PBO; Week 16 and all scheduled visits in Induction Period	Key secondary analysis: 2, 4, and 16 for ITT with Baseline Pruritus NRS score at least 4. Secondary analysis: other timepoints and population

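### Escape Arm summaries have no failure rule for patients removed at the 8-week EASI-50 check, so on an observed-case reading all later results are conditional on week-8 response

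*SAP*

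**What the plan says.** **Removal rule.** SAP 5.1.3.2: "Patients not achieving an EASI-50 response in the Escape Arm after 8 weeks of treatment will be terminated from the study". Protocol 3 agrees. Protocol 5.3.3 is wider and applies to patients "not achieving or maintaining an EASI50 score after 8 weeks of treatment will be terminated from the trial".

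**Planned summaries.** SAP 6.1.3.3: "For Maintenance W16 Escape Population, the number and percentage of patients achieving or maintaining a categorical efficacy and health outcome responses will be summarized" at all scheduled visits to Week 52, together with n, mean and SD for selected continuous measures. For the Week 24-48 Escape Population, "the number and percentage of patients regaining EASI-50 response or achieving EASI-75 will be summarized every 4 weeks". In Table KGAB.6.12 the escape rows have estimand NA and descriptive statistics only. The Week 24-48 rows cover IGA, pruritus and "Proportion of patients with EASI-75 after lebrikizumab retreatment"; neither escape population has an EASI-50 row.

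**Missing-data rules elsewhere.** On multiple imputation, SAP 6.4.2.1 says: "The imputation and analysis will be conducted on Maintenance Primary Population only". All four maintenance estimands in SAP 6.2.2 name that same population; the composite one, for example, has "Population: Maintenance Primary Population as described in Section 6.1.1". Under the non-responder rule in SAP 6.4.2.2, patients who "discontinue treatment, or transfer to escape arm will be set to non-response subsequent to this time through Week 52". Table KGAB.6.11 treats EASI, IGA and pruritus responses as missing whenever the baseline or visit value is missing.

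**The concern.** The design takes failures out of the arm at 8 weeks, and the SAP then tabulates the arm by visit without saying what happens to them. After the check (Week 28 onward for Week 16 entrants, 12 weeks onward for later entrants), an observed-case table describes only patients already shown to have EASI-50. A percentage can rise between 8 and 12 weeks because failures have left the denominator, with no patient improving.

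These summaries are the trial's evidence on two questions that its design raises: what continued treatment does for Week 16 non-responders, and whether responders who relapse can be recaptured. Removal may also differ between the prior-lebrikizumab and prior-placebo columns, which would distort their side-by-side reading.

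The planned disposition tables do not readily correct this. SAP 6.7 tabulates Maintenance Period discontinuation by reason only for the Maintenance Primary and Secondary Populations. The early-termination reasons in Protocol 8.7.1 do not include failing the Escape Arm check.

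**Working it through.** The documents give no figure for the Escape Arm, so there is none to reproduce.

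**1. Does any rule cover removed patients?** Multiple imputation and the four maintenance estimands are confined to the Maintenance Primary Population. The non-responder rule of 6.4.2.2 counts transfer to escape as failure, so applied inside the arm it would score every Week 24-48 escaper as a non-responder at every visit. That leaves Table KGAB.6.11, under which a removed patient's later response is missing.

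**2. How many patients are involved?** Inputs from SAP 5.2: about 400 patients, 2:1, EASI-75 48.0% versus 11.5%. Assume the EASI-75 rate is the responder rate and there is no dropout.
- Lebrikizumab: 266.7 × (1 - 0.480) = 138.7
- Placebo: 133.3 × (1 - 0.115) = 118.0
- Total: about 257 of 400 (64%)

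The same rates put 266.7 × 0.480 = 128 patients in the Maintenance Primary Population. Responders also qualify through IGA 0/1, so 257 is on the high side. In the extreme case of no overlap between IGA and EASI-75 responders (34.7% and 7.7% added), entrants would be 266.7 × 0.173 + 133.3 × 0.808 = 46.1 + 107.7, about 154.

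**3. How large is the effect on later response rates?** Let N enter, let a fraction f be removed at 8 weeks, and let R respond at a later visit, all among those remaining. Ignore other dropout.
- Observed-case rate: R / [(1-f)N]
- All-entrant rate: R / N
- Ratio: 1/(1-f)

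The values of f are assumptions. The last two columns assume that 60% of remaining patients have EASI-75.

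| f | Removed, of 257 | Ratio | Observed-case EASI-75 | All-entrant EASI-75 |
|---|---|---|---|---|
| 20% | 51 | 1.25 | 60% | 48% |
| 40% | 103 | 1.67 | 60% | 36% |
| 60% | 154 | 2.50 | 60% | 24% |

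**4. EASI-50 itself.** Let s be the chance of keeping EASI-50 from one 4-week visit to the next (assumed 0.85 to 1.00). At 12 weeks the observed-case rate is s and the all-entrant rate is (1-f)s. With s = 0.95 this is 95% against 76% (f = 20%) or 57% (f = 40%). Later values depend on which removal wording applies:
- Patients removed whenever they lose EASI-50: the observed-case rate stays at s, that is 85-100%.
- One check at 8 weeks, with losses that persist: it falls to s^5 by 28 weeks, 0.95^5 = 77% or 0.85^5 = 44%.

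**5. Which time points are touched?** Removal follows the 8-week assessment, so 4- and 8-week results are unaffected by this rule. Entrants at Weeks 24, 32, 40 and 48 have at most 28, 20, 12 and 4 weeks before Week 52. Week 48 entrants never reach the check. Their absence from later time points is administrative, not failure.

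**The case against.** The strongest reply is that inflation is not established. Table KGAB.6.1 defines each escape population as everyone who entered it (for Week 16 entrants, everyone also dosed), and 6.1.3.3 asks only for a number and percentage of patients. If that population is the denominator, removed patients simply do not count as responders and the bias in the percentages disappears. This stands as far as it goes: the inflation depends on the observed-case reading. But Table KGAB.6.11 points to that reading, and no text points to the other. By-visit means have no full-denominator reading at all.

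The results are also descriptive, carry no inferential statistics and lie outside multiplicity control. Continuous summaries show n at each visit, and SAP 6.7 lists every discontinuation from study treatment with its reason and timing. This limits the consequence, although a listing does not repair a percentage.

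A reader might infer more than the documents support:
- **That EASI-50 would be close to 100% by construction from 12 weeks.** This needs an observed-case denominator plus high persistence or repeated removal. A patient who loses EASI-50 is still counted as a failure at that visit, and step 4 shows values well below 100% with a single check. EASI-50 is also named only for the Week 24-48 population.
- **That all recapture results are affected.** The 4- and 8-week results are not affected by this rule.
- **That all 257 Week 16 entrants inform longer treatment of lebrikizumab non-responders.** About 118 of them come from placebo and start lebrikizumab at entry.

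**Conclusion.** The point holds in a limited form. The SAP has no denominator and no failure rule for either escape population, and its own definition of a missing response leads to observed-case results. On that reading, percentages after the 8-week check are inflated by about 1/(1-f), 1.25-fold at f = 20% and 1.67-fold at f = 40%, and means are selected for response. The size rests on an assumed f, no other dropout, and removed patients counting as non-responders.

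The Week 16 Escape Population may be the largest maintenance group: about 257 against 128 in the Maintenance Primary Population on the planning rates, with the caveats above. Primary and multiplicity-controlled analyses are untouched. This is more than missing detail, because the design itself creates the selection and a simple scoring rule removes it from the response percentages.

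**What to change.** In SAP 6.1.3.3 and Table KGAB.6.12:

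1. Report EASI-50, EASI-75, IGA 0/1 and pruritus response with all patients who entered the escape population as denominator, keeping the baseline-pruritus restriction for the itch endpoint. Add the missing EASI-50 rows.
2. For the Week 24-48 population, use at each time point the entrants whose entry visit allows it by Week 52. Keep administrative end of follow-up separate from failure.
3. Count patients terminated under the EASI-50 rule, or discontinued for lack of efficacy, as non-responders at later visits. State the handling of other dropout and of rescue use.
4. Write this as a new escape-specific rule. Do not cite 6.4.2.2, which scores transfer to escape as failure.
5. Show observed-case percentages and means alongside with n, labelled as conditional on remaining in the arm.
6. Report the number terminated under the 8-week rule by prior treatment.
7. Reconcile Protocol 5.3.3 (achieving or maintaining) with SAP 5.1.3.2 (achieving), since the interpretation of later visits depends on which applies.

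The cost is SAP wording and a few extra descriptive tables, with no new data. The reported rates would be less favourable.

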6.1.4. General Considerations for Safety Analyses for Combined Induction and Maintenance Periods

Adverse event, exposure summary, and categorical laboratory/vital sign changes will be provided for the All Lebrikizumab Safety Population during the Combined Induction and Maintenance Periods. For patients who were first exposed to lebrikizumab during Induction Period, the baseline for TEAE will utilize the baseline for Induction Period defined in Section 6.1.2; for patients who were first exposed to lebrikizumab during Maintenance Period, the baseline for TEAE will utilize the baseline for Maintenance Period defined in Section 6.1.3.

More details on baseline and postbaseline definitions can be found in the Compound Level Safety Standard.

6.1.5. General Considerations for Safety Analyses for Combined Induction and Maintenance Periods Plus Follow Up Period

Selective AE summaries will be provided for the All Lebrikizumab Safety Population during the Combined Induction and Maintenance Periods plus Follow up Period. The baseline definition

for this population is the same as Section 6.1.4. More details on baseline and postbaseline definitions can be found in the Compound Level Safety Standard.

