**Table 3: Escape Arm Dosing Schedule by Treatment Group**

Induction Group Assignment	Maintenance Treatment Assignment	Maintenance Loading Dose (Blinded)	Week 20 to 50 (Unblinded: 250mg Q2W)
Patients entering Escape Arm at Week 16			
Active	Escape arm	Week 16: one active and one placebo injection Week 18: one active and one placebo injection	One active injection
Placebo	Escape arm	Week 16: two active injections Week 18: two active injections	One active injection
Patients entering Escape Arm at Week 24, 32, 40 and 48			
	Lebrikizumab 250 mg Q2W	At entry: one active and one placebo injection At next administration: one active and one placebo injection	One active injection
	Lebrikizumab 250 mg Q4W	At entry: one active and one placebo injection At next administration: one active and one placebo injection	One active injection
	Placebo	At entry: two active injections At next administration: two active injections	One active injection

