Maintenance W16 Escape Population	Including patients who were NOT re-randomized to Lebrikizumab 250 mg Q2W, Lebrikizumab 250 mg Q4W or placebo but assigned to escape arm at Week 16, and received at least one dose of study treatment during the maintenance period. Selective efficacy analyses for the maintenance period will be conducted on the Maintenance W16 Escape Population.
Maintenance W24-48 Escape Population	Including patients from Maintenance Primary and Secondary Population who escaped to Lebrikizumab 250 mg Q2W due to EASI-50 non-response at Week 24, 32, 40 or 48. Selective efficacy analyses for the maintenance period will be conducted on the Maintenance W24-48 Escape Population
All Lebrikizumab Safety Population	All randomized patients who received at least 1 dose of lebrikizumab treatment during Combined Induction and Maintenance Periods. Safety analyses for the Combined Induction and Maintenance Periods will be conducted on All Lebrikizumab Safety Population. Selective safety analyses for the Combined Induction and Maintenance Periods plus the follow-up Period will be conducted on All Lebrikizumab Safety Population.

Abbreviations: EASI = Eczema Area and Severity Index; IGA = Investigator Global Assessment;

Table KGAB.6.2. Treatment Groups and Comparisons for Each Study Period and Analysis Population

Study Period	Analysis Population	Treatment Groups	Abbreviation	Inferential Comparisons When Applicable
Induction Period	ITT; Safety	Placebo; Lebrikizumab 250 mg Q2W	PBO; LEB250Q2W	LEB250Q2W vs PBO
Maintenance Blinded Period	Maintenance Primary Population	Lebrikizumab_Res/Placebo; Lebrikizumab_Res/Lebrikizumab 250 mg Q4W; Lebrikizumab_Res/Lebrikizumab 250 mg Q2W; Total Lebrikizumab_Res/ Lebrikizumab (Safety analysis only)	LEB_Res/PBO; LEB_Res/LEB250Q4W; LEB_Res/LEB250Q2W; Total LEB_Res/LEB (Safety analysis only)	LEB_Res/LEB250Q4W vs LEB_Res/PBO; LEB_Res/LEB250Q2W vs LEB_Res/PBO
Maintenance Blinded Period	Maintenance Secondary Population	Placebo_Res/Placebo; Placebo_Res/Lebrikizumab 250 mg Q4W; Placebo_Res/Lebrikizumab 250 mg Q2W	PBO_Res/PBO; PBO_Res/LEB250Q4W; PBO_Res/LEB250Q2W	No Between-Group or Overall Comparisons
Maintenance Escape Period	Maintenance W16 Escape Population	Lebrikizumab_NonResp/ Lebrikizumab 250 mg Q2W; Placebo_NonResp/Lebrikizumab 250 Q2W	LEB_NonResp/ LEB250Q2W; PBO_NonResp/ LEB250Q2W	No Between-Group or Overall Comparisons

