Maintenance Escape Period	Maintenance W24-48 Escape Population	Lebrikizumab 250 mg Q2W/Placebo/ Lebrikizumab 250 mg Q2W; Lebrikizumab 250 mg Q2W/Lebrikizumab 250 mg Q4W/Lebrikizumab 250 mg Q2W; Lebrikizumab 250 mg Q2W/Lebrikizumab 250 mg Q2W/Lebrikizumab 250 mg Q2W; Placebo/Placebo/Lebrikizumab 250 mg Q2W; Placebo/Lebrikizumab 250 mg Q4W/Lebrikizumab 250 mg Q2W; Placebo/Lebrikizumab 250 mg Q2W/Lebrikizumab 250 mg Q2W	LEB250Q2W/PBO/LEB250Q2W ; LEB250Q2W/ LEB250Q4W/ LEB250Q2W; LEB250Q2W/ LEB250Q2W/ LEB250Q2W; PBO/PBO/LEB250Q2W; PBO/LEB250Q4W/LEB250Q2W ; PBO/LEB250Q2W/LEB250Q2W	No Between-Group or Overall Comparisons

Treatment Groups and Comparisons for Each Study Period and Analysis Population

Study Period	Analysis Population	Treatment Groups	Abbreviation	Inferential Comparisons When Applicable
Combined Induction and Maintenance Periods	All Lebrikizumab Safety Population	Any Lebrikizumab	N/A	No Between-Group or Overall Comparisons
Combined Induction and Maintenance Periods + FU	All Lebrikizumab Safety Population	Any Lebrikizumab	N/A	No Between-Group or Overall Comparisons

Abbreviations: FU = follow-up; ITT = intent-to-treat; LEB = lebrikizumab; NonResp = non-responder; PBO = placebo; Q2W = every 2 weeks; Q4W = every 4 weeks; Res = responder.

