6.1.3. General Considerations for Analyses During Maintenance Period

Maintenance Period starts at the first injection of study treatment at Week 16 and ends on the date of Week 52 or the ETV (between Weeks 16 and 52) unless specified otherwise.

For the efficacy and health outcome analyses, baseline is defined as the last available value before the first injection in Induction Period and, in most cases, will be the value recorded at Baseline Visit (Day 1).

Unless otherwise specified, efficacy and health outcome scores at Week 16 prior to entering Maintenance Period will be presented for the visitwise reports for Maintenance Period.

Unless specified otherwise, for the safety analyses during Maintenance Period, baseline is defined as the last available value before first injection in Maintenance Period. In most cases, this will be the measure recorded at Week 16. For TEAEs, baseline is the events ongoing just prior to the first injection of the study drug injection at Week 16.

For patients in the Maintenance Primary and Secondary Population who met escape criteria (EASI-50 nonresponse) and escaped to lebrikizumab 250 mg Q2W at Weeks 24, 32, 40 and 48, only data in the Maintenance blinded period (up to the time of escape) will be included in both efficacy and safety analyses.

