The exposure for the All Lebrizumab Safety Population during the Combined Induction and Maintenance Periods will be calculated as (Date of last study visit during Treatment Period – Date of first lebrizumab injection + 1 day) calculated for each treatment period where the patient receives lebrizumab and then summed together (this excludes the duration of time that patients are receiving placebo during the Maintenance Period). If a patient was randomized to lebrizumab during Induction Period, then to placebo during Maintenance Period and later on entered escape arm following loss of response (<EASI-50), the patient’s exposure on lebrizumab during Maintenance Period will be calculated (Date of last study visit during Maintenance Period – Date of first injection to resume lebrizumab + 1 day) and will be added to the exposure in the Induction Period.

The exposure for the All Lebrizumab Safety Population during the Combined Induction and Maintenance Periods plus Follow up Period will be calculated as the time between the first dose of LY and the study treatment disposition visit plus any follow-up period.

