6.14.2. Adverse Events

A TEAE is defined as an event that first occurred or worsened in severity after baseline. The MedDRA Lowest Level Term (LLT) will be used in the treatment-emergent computation. The maximum severity for each LLT during the baseline period will be used as baseline. The treatment period will be included as postbaseline for the analysis. For events with a missing severity during the baseline period, it will be treated as ‘mild’ in severity for determining treatment-emergence. Events with a missing severity during the postbaseline period will be treated as ‘severe’ and treatment-emergence will be determined by comparing to baseline severity. For events occurring on the day of first taking study medication, it will be assumed to be posttreatment.

The planned summaries for adverse events are provided in [Table KGAB.6.13](#), and are described more fully in compound level safety standards and in the adverse event-related PhUSE white paper [Analysis and Displays Associated with Adverse Events: Focus on Adverse Events in Phase 2-4 Clinical Trials and Integrated Summary Document (PhUSE 2017)].

Summary tables as described in [Table KGAB.6.13](#) will be presented for the following periods/analysis populations as indicated. Summary tables will include the number and percentage of patients reporting an event. For events that are gender-specific (as defined by MedDRA), the number of participants at risk will include only patients from the given gender.

- Induction Period (Safety Population, S)
- Maintenance Blinded Period (Maintenance Primary Population, M)
- Combined Induction Period and Maintenance Period, Combined Induction and Maintenance Periods Plus Follow-Up Period [selective analysis] (All Lebrizumab Safety Population, A)

Table KGAB.6.13. Summary Tables/Listing Related to Adverse Events

Analysis	Population (Section 6.1.1)
Overview of AEs	S, M, A
Summary of TEAE by PTs	S, M
Summary of TEAE by PTs occurring in $\geq 1\%$ of patients	S, M
Summary of TEAE by PTs within SOC	S, M, A
Summary of TEAE PTs by maximum severity	S, M
Summary of SAE by PT within SOC	S, M, A
Summary of AEs leading to treatment discontinuation by PT with SOC	S, M, A
Summary of TEAE possibly related to study drug by PTs within SOC	S, M
Listing of SAEs (including Death)	ITT
Listing of primary AEs leading to study treatment discontinuation	ITT
Listing of TEAE (for Japan submission only)	S

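### The Week 16 TEAE baseline in SAP 6.1.4 counts placebo-period events as lebrikizumab TEAEs for the few patients whose first lebrikizumab comes at a Week 24 to 48 escape

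*SAP*

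**What the plan says.** SAP 6.1.4 gives the All Lebrikizumab Safety Population two TEAE baselines. Patients first exposed in Induction take the Induction baseline; the others follow this rule: "for patients who were first exposed to lebrikizumab during Maintenance Period, the baseline for TEAE will utilize the baseline for Maintenance Period". SAP 6.1.3 defines the second one: "For TEAEs, baseline is the events ongoing just prior to the first injection of the study drug injection at Week 16". SAP 5.1.3 places the escape period inside the Maintenance Period, so first exposure at escape falls under this rule. No baseline is set at escape. SAP 6.1.5 takes over the same definition for the analysis that adds follow-up.

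SAP 6.14.2 states that "A TEAE is defined as an event that first occurred or worsened in severity after baseline" and that "The treatment period will be included as postbaseline for the analysis". It does not remove placebo time.

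Membership of the population requires a single lebrikizumab dose (Table KGAB.6.1: "All randomized patients who received at least 1 dose of lebrikizumab treatment during Combined Induction and Maintenance Periods"). Table KGAB.6.2 lists the sequence "PBO/PBO/LEB250Q2W" among the escape groups and reports the whole population in one column. For patients escaping from maintenance placebo, Protocol Table 3 has active drug beginning at escape: "At entry: two active injections At next administration: two active injections".

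For exposure in the same population over the combined periods, SAP 6.14.1 counts from the first lebrikizumab injection and adds that "this excludes the duration of time that patients are receiving placebo during the Maintenance Period".

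**The concern.** For one treatment sequence, the baseline date and the date of first exposure come apart. A patient on placebo in Induction, on placebo again after Week 16, and then moved to lebrikizumab at escape is judged for treatment emergence from Week 16. An event starting at Week 20 would be new after baseline, and so a lebrikizumab TEAE, although the patient had not yet received lebrikizumab. The exposure rule for the same patient starts later, so the two summaries describe different periods.

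At stake is the pooled lebrikizumab safety column. These patients escape because they lost EASI-50 on placebo, so their pre-escape time is when worsening disease would be expected. SAP 6.14.6 tabulates skin infections and atopic dermatitis exacerbation for this same population. In a pooled table, a few misattributed serious or special-interest events can draw attention.

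**Working it through.** The plan gives no figure of its own on this point. The check is a trace of the text, then a count of days and patients.

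**Which patients are affected**

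| Sequence | First lebrikizumab | TEAE baseline under 6.1.4 | Baseline at first lebrikizumab? |
|---|---|---|---|
| Lebrikizumab in Induction | Day 1 | Induction | Yes |
| Placebo responder re-randomised to lebrikizumab | Week 16 | Week 16 | Yes |
| Placebo non-responder escaping at Week 16 | Week 16 | Week 16 | Yes |
| Placebo, placebo, then escape | Week 24, 32, 40 or 48 | Week 16 | No |

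SAP 6.1.3 uses only data up to escape for the Maintenance Primary and Secondary Populations. That limit does not apply to the All Lebrikizumab Safety Population, so it does not remove the problem.

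**Length of the mismatch**, for a patient followed to Week 52

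- TEAE window from Week 16: 36 × 7 + 1 = 253 days.
- Placebo days before lebrikizumab, escape at week w: (w − 16) × 7.
- Exposure under 6.14.1: (52 − w) × 7 + 1.

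| Escape week | Placebo days inside the TEAE window | Exposure days | TEAE window ÷ exposure |
|---|---|---|---|
| 24 | 56 | 197 | 253/197 = 1.28 |
| 32 | 112 | 141 | 253/141 = 1.79 |
| 40 | 168 | 85 | 253/85 = 2.98 |
| 48 | 224 | 29 | 253/29 = 8.72 |

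**Number of patients**

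Inputs: 400 patients randomised 2:1, so 400/3 = 133.3 on placebo (SAP 5.2); planning placebo rates of 11.5% for EASI-75 and 7.7% for IGA 0 or 1 (SAP 5.2); re-randomisation 2:2:1, so 1 in 5 responders goes to placebo (SAP 5.1.3). The 30% upper value is my assumption, to allow for a higher placebo response and because either criterion qualifies a responder.

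Formula: 133.3 × response rate ÷ 5.

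- 7.7%: 10.3 responders, 2.05 to placebo (0.5% of 400).
- 11.5%: 15.3 responders, 3.07 to placebo (0.8% of 400).
- 30%: 40.0 responders, 8.0 to placebo (2.0% of 400).

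These are ceilings. A patient must also lose EASI-50 and escape, and then contributes a misplaced TEAE only if an event arose or worsened between Week 16 and escape.

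**The case against.** The strongest reply is that SAP 6.1.4 sends the reader to the Compound Level Safety Standard for more detail on baseline and postbaseline definitions. That standard is not in the file and might limit the postbaseline window to time on lebrikizumab. This stands as a reason to check it. It does not remove the point: the SAP states its own baseline rule, cites the standard only for further detail, and lets the standard supersede the SAP only for special safety topics (SAP 6.14.6).

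The second reply is that the effect is negligible, in a descriptive column for which Table KGAB.6.2 plans no comparisons. The size is conceded. It bears on how much the point matters, not on whether the count is right.

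Two stronger readings are tempting, and the documents do not support them.

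- A reader might infer that the lebrikizumab event rate is inflated because events are divided by too little exposure. SAP 6.14.2 specifies numbers and percentages of patients and no rate per patient-year. Exposure is a separate descriptive summary.
- A reader might extend the point to lebrikizumab responders re-randomised to placebo, whose placebo time is also excluded from exposure under the combined-period rule. These patients have already had 16 weeks of lebrikizumab, so keeping their later events in an ever-exposed population is defensible. They already have their own arm in the main adverse event tables for the Maintenance Primary Population. The exposure rule that adds follow-up, as worded, does not subtract their placebo time. How to display those events is a preference, not an error.

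**Conclusion.** The point holds for one sequence only: placebo in Induction, placebo after re-randomisation, first lebrikizumab at a Week 24 to 48 escape. For these patients the SAP as written counts events that precede any lebrikizumab as lebrikizumab TEAEs, and its exposure rule covers a different period.

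The size is about 3 patients at planning rates and about 2 to 8 across placebo response of 7.7% to 30%, before requiring escape. This rests on 400 patients, the planning response rates and the 2:2:1 ratio. The consequence is confined to descriptive counts and percentages in the pooled lebrikizumab column. The comparative safety analyses, in the Safety Population during Induction and in the Maintenance Primary Population, do not use these patients' maintenance events. Whether the final tables would carry the error depends also on the Compound Level Safety Standard, which could not be checked.

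**What to change.** In SAP 6.1.4, and so in 6.1.5, add a rule for patients whose first lebrikizumab injection comes after Week 16. Their TEAE baseline is the set of events ongoing just before that injection, parallel to 6.1.3, and only events with onset or worsening on or after it are counted. This matches the start of exposure in 6.14.1.

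The baseline should be limited to ongoing events. SAP 6.14.2 takes the maximum severity per lowest level term over the baseline period. If all earlier placebo time served as baseline, an event that had resolved on placebo could mask a recurrence of the same severity on lebrikizumab.

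Confirm that the Compound Level Safety Standard says the same. The cost is one sentence in the SAP and one date comparison in programming. No endpoint, test or data collection changes.
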